#### **4.3.7 Secondary Endpoint Analysis:**

Glucose levels below target range will be measured and analyzed as the mean decremental area over the curve (AOC(0-5hrs) in minutes\*mg/dL) during exercise. AOC will be estimated using Trapezoidal Rule.

Analysis will be conducted for glucose levels below range (interstitial glucose  $\leq 70$  mg/dL (3.89 mmol/L), interstitial glucose between 54-70 mg/dL (3 – 3.89 mmol/L),  $<54$  mg/dL (3 mmol/L)) using a contingency table and treatment difference will be calculated using Chi square/Fisher's exact test.

Proportional time (percentage within serious hypoglycemia <54 mg/dL (3 mmol/L)) will be calculated and treatment difference will be calculated using ANOVA/Kruskal–Wallis test, based on whether the data is normally distributed or not respectively.

Insulin utilization as reported by subjects in Outpatient phase and change from baseline will be analyzed using ANOVA.

The Questionnaires will be analyzed using T Test/ANOVA for CRC/outpatient phase. For ANOVA, significant value will lead to a post hoc analysis for identifying the treatment pairs which are significantly different.

Changes from baseline in questionnaire values (numeric) will be analyzed by the ANCOVA model using treatment arm at Outpatient phase, treatment sequence in CRC phase, sex as factors with age, weight and baseline value as covariates.

Example of SAS syntax code that can be used for secondary endpoint analysis is provided in APPENDICES 2.

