### 1.3 DETERMINATION OF SAMPLE SIZE

The primary endpoint of the study is the incidence of hypoglycemia (glucose  $\leq$  70 mg/dL (3.89 mmol/L)) associated with an exercise session, which occurred within the 12-week outpatient follow-up, as measured by BGM. The null hypothesis is that there is no difference between the treatment groups in the incidence of exercise-associated hypoglycemia, and the alternative is there is a difference between the treatment groups in terms of the incidence of exercise-associated hypoglycemia. With an effect size estimate of 0.262 (variance of means 59, common standard deviation 15), 80% power and an alpha of 0.05, using a one-way analysis of variance, 14 subjects per treatment group in the Outpatient Stage is required. Accounting for 15% attrition, a total of 48 subjects will be randomized.

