#### Secondary Endpoints:

1. Interstitial glucose (IG) levels below target range, measured by unblinded CGM (inpatient and outpatient), defined as both time (in minutes) and mean decremental area over the curve (AOC (0-300 min) in minutes\*mg/dL) during exercise:
  - Below range, as defined by  $IG \leq 70 \text{ mg/dL} (\leq 3.89 \text{ mmol/L})$

- Below range, as defined by IG between 54 to 70 mg/dL (3–3.89 mmol/L)
- Below range, as defined by IG < 54 mg/dL (<3 mmol/L)
- Proportional time (percentage time within hypoglycemia IG  $\leq$  70 mg/dL (3.89 mmol/L) and clinically significant hypoglycemia IG < 54 mg/dL (3mmol/L)).

2. Insulin utilization as reported by subject at baseline, and weeks 4, 8 and 12 in the outpatient setting.
3. Change from Baseline to the end of the Outpatient Phase in PROs: Barriers to Physical Activity in Diabetes (Type 1) (BAPAD-1), Hypoglycemia Fear Survey (HFS-II), and Hypoglycemic Confidence Scale (HCS).

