#### **4.3.6 Primary Endpoint Analysis:**

The primary efficacy hypothesis test for the study is as follows:

Null Hypothesis: There is no difference between the treatment groups in the mean incidence of hypoglycemia (glucose  $\leq 70$  mg/dL (3.89 mmol/L)) associated with an exercise session occurring within the 12 weeks of out-patient treatment as measured by BGM.

Alternative Hypothesis: There is a difference between treatment groups in the mean incidence of hypoglycemia (glucose  $\leq 70$  mg/dL (3.89 mmol/L)) associated with an exercise session occurring within the 12 weeks of out-patient treatment as measured by BGM.

Incidence rate per subject is calculated by summing the number of exercise sessions completed within 12 weeks and dividing this denominator by the number of hypoglycemic events that

occurred during those exercise sessions (Incidence Rate = number of exercise sessions / inter/post-exercise hypoglycemic events). Events associated with an exercise session are defined as hypoglycemic events that occur during or within 30 minutes of exercise completion.

The primary efficacy analysis will be analyzed by ANOVA comparing the mean incidence rate between the three treatment groups. All statistical significance testing will be two-sided with a p-value  $<0.05$ . Efficacy endpoints will be analyzed using the ITT and PP analysis populations for Outpatient phase, if performed F-test yields an overall p-value less than 0.05 ( $p<0.05$ ), post-hoc analysis of groups means will be conducted to statistically determine which group means differ.

Parameters that do not meet normality criterion will be analyzed non-parametrically. Overall treatment effect will be assessed using Friedman's test. If the overall treatment effect is significant in the Friedman's test, pairwise treatment comparisons will be assessed using the following tests.

- If the difference between two treatments is normally distributed (i.e., the p-value is  $\geq 0.05$  for Shapiro-Wilk test, the Tukey Test will be used.
- If the difference between two treatments is not normally distributed and the distribution is highly skewed, then the sign test/Kruskal Wallis test will be used.

Example of SAS syntax code that can be used for primary endpoint analysis is provided in APPENDIX 1.

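### SAP 4.3.7 sends CGM time and area below range to a chi-square/Fisher table and names no between-arm test for most of the measures that define the endpoint

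*SAP*

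**What the plan says.** SAP section 3 (Secondary Endpoints) lists first the interstitial glucose levels below range, "measured by unblinded CGM (inpatient and outpatient), defined as both time (in minutes) and mean decremental area over the curve" over 0-300 minutes. There are three bands: ≤70, 54-70 and <54 mg/dL. A further line adds "Proportional time (percentage time within hypoglycemia IG" ≤70 mg/dL and the same percentage for <54 mg/dL. Protocol 5.2.2 has the same definition and calls the endpoint key secondary.

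SAP 4.3.7 then does three things:

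- It estimates the area by the trapezoidal rule and names no test for it.
- It analyzes the three bands "using a contingency table and treatment difference will be calculated using Chi square/Fisher" (the exact test).
- It gives ANOVA/Kruskal-Wallis to "Proportional time (percentage within serious hypoglycemia" below 54 mg/dL, and to nothing else in this endpoint.

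Protocol 12.4.3 names no test for these measures. SAP 5.1 lists tables for glucose below range (14.2.4.5.1.x and 14.2.4.5.2.x) and for time within hypoglycemia (14.2.4.5.3.x and 14.2.4.5.4.x), without a method. SAP 4.3.8 assigns ANOVA/Kruskal-Wallis to both time and percent time for the exploratory in-range, >180 and >250 mg/dL bands.

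**The concern.** Minutes and area are continuous. A contingency table can use them only after each is cut to a yes/no or a category, and the SAP does not say how. The quantity tested is then no longer the quantity defined. The less important exploratory bands get the fitting method, while the key secondary bands do not.

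An outpatient subject contributes many exercise sessions. If each subject is scored as having had any low or none, a subject with one brief low and a subject with lows in half the sessions count the same. For a common event such as ≤70 mg/dL, most subjects in every arm become positive and the arms look alike. A real reduction in hypoglycemia could then appear as no difference in the main CGM support for the secondary objective on prevention of hypoglycemia.

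The endpoint also covers the inpatient phase. There each subject receives both treatments, and an ordinary chi-square or Fisher test ignores that pairing.

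**Working it through.** **The plan's own figure.** The SAP sizes only the primary endpoint: "With an effect size estimate of 0.262 (variance of means 59, common standard deviation 15), 80% power and an alpha of 0.05". With λ = 3n × 59/225 and a noncentral F on 2 and 3(n−1) degrees of freedom, n = 13 gives 78.9% power and n = 14 gives 82.3%. This reproduces "14 subjects per treatment group in the Outpatient Stage is required". No figure is given for the CGM endpoint, so 14 per arm is used below.

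**Which measures have a fitting test.**

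| Measure | ≤70 | 54-70 | <54 |
|---|---|---|---|
| Decremental area | none named | none named | none named |
| Minutes | none named | none named | covered through percent time, if the 300-minute window is complete |
| Percent time | none named | not an endpoint | ANOVA/Kruskal-Wallis |

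The one covered cell follows because percent time = 100 × minutes/300 in a complete window, which is only a rescaling.

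**Inputs for the size of the loss.**

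- Sessions per subject: 2-3 per week (Protocol 8.4) × 12 weeks = 24-36.
- Session risk of ≤70 in the insulin-reduction arm: 5/15 = 33%, from the crossover pilot study in Protocol 4.2. Half of that, 16.5%, is assumed in both glucagon arms.
- Within-subject correlation (ICC): not in the documents. 0.10 is assumed for power, and 0.05-0.20 for ranges.

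**Share of subjects with any low.** Let subject risk follow a beta distribution with a = p(1/ICC − 1) and b = (1 − p)(1/ICC − 1). Then P(any) = 1 − B(a, b+m)/B(a, b) for m sessions. At ICC 0.10:

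- p = 0.33 (a = 2.97, b = 6.03): 98.8% at 24 sessions, 99.6% at 36.
- p = 0.165 (a = 1.485, b = 7.515): 87.7% at 24 sessions, 92.3% at 36.

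At 24 sessions the table expects about 13.8 of 14 positives against 12.3 of 14, although the session risk has halved.

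**Power**, simulated with three arms of 14, ICC 0.10 and two-sided 5%. Kruskal-Wallis is applied to each subject's number of positive sessions, as a stand-in for minutes.

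| Session risk, control vs both glucagon arms | Any/none chi-square | Kruskal-Wallis |
|---|---|---|
| 33% vs 16.5%, 24 sessions | 9% | 79% |
| 33% vs 16.5%, 36 sessions | 6% | 83% |
| 20% vs 10%, 24-36 sessions | 15-23% | 56-60% |
| 33% vs 10%, 24-36 sessions | 23-41% | 99% or more |

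Repeat runs of the 33% vs 16.5% case give about 6-11% against 78-84%. Kruskal-Wallis on one value per subject held its type I error at 4.0-5.4% in every null setting tried.

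**Rarer events.** At 5% session risk, which might suit <54 mg/dL, P(any) is 34-65% for ICC 0.05-0.20 and 24-36 sessions. The table is then not saturated. At 5% vs 2.5% with ICC 0.10, the same simulation gives both tests about 18-21% power, so on this stand-in little is lost.

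**If sessions were counted instead.** The design effect is 1 + (m−1) × ICC, and the true type I error of a nominal 5% test on 2 degrees of freedom is exp(−5.99/(2 × design effect)).

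- m = 24, ICC 0.05: 1 + 23 × 0.05 = 2.15, error 25%.
- m = 36, ICC 0.20: 1 + 35 × 0.20 = 8.0, error 69%.

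**The case against.** The best defense is that the plan can be read sensibly. SAP section 2 says that counts in summary tables of categorical variables are numbers of subjects and never exceed the number in the group. Read that way, the table has one entry per subject and its type I error is controlled. Time below range is not dropped either, since tables for it are listed. The primary objective rests on meter readings, not CGM, and this is a Phase 2 study of preliminary efficacy.

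Most of this stands, and it rules out several stronger readings that a reader might infer:

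- **That the outpatient p-values are invalid.** The 25-69% error rate needs sessions as the counted unit. The SAP does not say so, and its only general convention points to subjects. The frequency-weighted example code in Appendix 2 is generic and settles nothing.
- **That the overlapping bands make the table incoherent.** The ≤70 band contains the other two, which distorts the test only if all three are columns of one table. The SAP does not say they are. Three separate tables would be redundant but sound.
- **That no stated measure gets a valid test.** Percent time <54 does, and with it minutes <54 over a complete window.
- **That practically every subject would be positive.** A figure of 99.5-100% at 20% session risk assumes independent sessions, since 1 − 0.8^24 = 0.995. With ICC 0.05-0.20 the share is 82-99%, and lower for rarer events.

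The defense does not supply the missing tests. A valid any/none comparison still does not test minutes or area, and listing a table does not name a method.

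**Conclusion.** The SAP prescribes a poorly matched test for the below-range bands. It leaves area in all bands, minutes ≤70 and 54-70, and percent time ≤70 without a named between-arm test. Counted by subject, the outpatient comparison is valid but weak for ≤70 mg/dL: about 6-11% power where a per-subject Kruskal-Wallis has about 78-84%. Those figures assume 24-36 sessions, ICC 0.10, session risk 33% vs 16.5% and 14 subjects per arm. The ICC and the treated-arm risk are not in the documents. The direction of the loss for common events does not depend on their exact values, but its size does, and for rare <54 events it may be small. In the CRC crossover, the unpaired test also ignores that each subject is his or her own control.

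This should be fixed, but it is not critical. It concerns a secondary endpoint, and neither the primary test nor the sample size changes.

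**What to change.** Replace chi-square/Fisher as the between-arm test for this endpoint in SAP 4.3.7.

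- **Outpatient Phase:** for each subject and each band (≤70, 54-70, <54 mg/dL), average minutes, decremental area and percent time over the analyzed sessions. Compare the three arms on these subject-level values by ANOVA or Kruskal-Wallis, as SAP 4.3.8 already does for time and percent time in the exploratory bands. Add percent time ≤70 to the existing <54 analysis.
- **CRC Phase:** use a within-subject crossover comparison, either the crossover t-test already coded in Appendix 2 or its rank equivalent.
- **If a contingency table is kept:** make it descriptive, state that it counts subjects, and use disjoint bands (54-70 and <54).

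The cost is SAP wording and the shells for tables 14.2.4.5.1.x to 14.2.4.5.4.x. No new data are needed. The change should be made before unblinding, so that the method is not chosen with results in view.

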### 1.2 STUDY DESIGN:

This study is a randomized, placebo-controlled, double-blind, two-treatment, two-period, crossover comparison in a clinical research center (CRC) setting, followed by a randomized, placebo-controlled, partially double-blinded, 3-arm parallel comparison in an outpatient setting to evaluate the preliminary efficacy and safety of Glucagon RTU to prevent exercise-induced hypoglycemia (EIH) in adults with Type 1 diabetes mellitus (T1D), who perform regular, moderate-to-high intensity aerobic exercise.

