#### 1.3.1 Randomization and Blinding

The study statistician will create the randomization schedule for the study. The randomization assignment for the subject will be conducted once at the time of enrollment and confirmation of eligibility. The CRC assignments will be by random assignment during the first session to either Glucagon RTU or Placebo. At the second session, the subject will be crossed over to the other treatment assignment. At the completion of the CRC visits, the subject will then have his/her treatment assignment applied for the parallel group study.

The cross-over study is blinded to the extent possible since all subjects will receive both Glucagon RTU and placebo. All staff, subjects and study team members will know that the subject will receive both study treatments during the CRC sessions. During the outpatient study, two of the treatments will be blinded to the study staff, subjects and Sponsor. One arm of the study will be open label. It is imperative for the study staff to remain blinded to treatment assignment prior to randomization and during the study treatment periods as not to bias the outcome.

Glucagon RTU and Placebo will be prepared and administered so that the two will be indistinguishable.

Blinding of study treatment is critical to the integrity of this clinical trial. It is expected that in the majority of cases, AEs can be properly managed without the need for unblinding. However, in the event of a medical emergency in which knowledge of an individual subject's treatment

assignment is considered critical to the subject's management, the treating physician may unblind the treatment assignment. The investigator should contact the responsible Medical Director to discuss the subject and circumstances requiring the unblinding. The blind will be broken only for the specific subject under discussion. The Sponsor will remain blinded to the treatment assignment. Every effort will be made to restrict knowledge of the treatment assignment to the investigator only.

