**Exploratory Endpoints:**

1. Mean time and mean proportional time (%) within range, as defined by IG between 70 and 180 mg/dL (3.89 to 10 mmol/L) (CGM, 0 to 300 minutes with exercise), across the 2 CRC treatment arms.
2. Time, proportional time (percentage), and mean incremental Area Under Curve, plasma glucose  $>$  180 mg/dL (10 mmol/L), and (AUC (0-300 min) in minutes\*mg/dL) during exercise, across the 2 CRC treatment arms and the 3 outpatient treatment arms.
3. The time, proportional time (percentage), and mean incremental area under the curve (AUC) during which plasma glucose  $>$ 250 mg/dL (AUC (0-300 min) in minutes\*mg/dL) during exercise, across the 2 CRC treatment arms and the 3 outpatient treatment arms.
4. Incidence of overnight hypoglycemia as measured by CGM, across the 2 CRC treatment arms and the 3 outpatient treatment arms.
5. Compare the glucose tablet utilization during exercise, across the 2 CRC treatment arms and the 3 outpatient treatment arms.

6. Compare food (carbohydrate) intake pre/post exercise, across the 3 outpatient treatment arms.
7. Compare number of exercise sessions performed across the 3 outpatient treatment arms.
  - a. Conduct subgroup analysis for:
    - i. comparison of the number of qualified exercise sessions out of total number of exercise sessions conducted
    - ii. comparison of the number of qualified sessions meeting less than 30% proportional time at target HR
    - iii. comparison of the number of qualified sessions meeting greater than or equal to 30% proportional time at target HR
8. Compare number of minutes of exercise performed per week, across the 3 outpatient treatment arms.
9. Compare caloric expenditure during exercise, across 3 treatment arms.
10. The change from Baseline to end of study in body weight will be measured and analyzed across the 3 treatment arms.
11. Compare number of steps taken, and the distance achieved during exercise sessions across the 3 outpatient treatments arms.
12. The following assessments during exercise sessions will be captured from the wearable activity monitor: heart rate, daily steps, calories burned, distance covered, floors climbed, active minutes.
13. Change from baseline in HbA1c.

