#### **4.3.8 Exploratory Analysis:**

Glucose levels within range, >180 mg/dl, >250 mg/dl will be measured and analyzed as the mean incremental area under the curve (AUC(0-5hrs) in minutes\*mg/dL) during exercise.

Time and Proportional time (percentage within range, >180 mg/dl, >250 mg/dl) will be calculated and treatment difference will be calculated using ANOVA/Kruskal–Wallis test, based on whether the data is normally distributed or not respectively.

Generally, unless otherwise stated, the mean incidence rates will be compared using the T tests/ ANOVA or ANCOVA models using treatment arm at Outpatient phase, treatment sequence, obtained by combining the received treatments at CRC and Outpatient phase, sex as factors with, if applicable, age and weight as covariates.

Glucose tablet utilization during exercise, food (carbohydrate) intake pre/post exercise, number of exercise sessions completed across the 3 outpatient treatment arms , number of minutes exercised per week, number of calories burned per exercise sessions, number of steps, distance

covered, heart rate, floors climbed and change from Baseline in body weight will be compared for the treatment arms using T tests/ ANOVA at CRC/ Outpatient phase.

Incidence of overnight hypoglycemia will be compared for the treatment arms using Chi-Square/Fisher's exact tests at CRC/ Outpatient phase.

HbA1c data will be summarized using descriptive statistics (n, mean, SD, median, min, and max) for each scheduled study assessment, as well as change from baseline, will be summarized using ITT and PP Population.

Example of SAS syntax code that can be used for exploratory analysis is provided in APPENDIX 3.

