#### 4.6.2 APPENDIX 2. Example of SAS syntax code for secondary endpoint analysis.

The following macro can be used for the calculation of area over the curve (AOC):

```
%macro auc (dsn);
  data auctree;
    set &dsn;
    if concentration = 0 and time > tlast then delete;
    x = time;
    y = concentration;
    xpre = lag(x);
    ypre = lag(y);
    xdif = x - xpre;
    if x <= tmax or y = ypre or y =0 or ypre = 0 then do;
      auc = xdif * (( y + ypre ) / 2 );*linear rule;
    end;
    else do;
      auc = xdif * ((y - ypre) / log (y / ypre));
    end;
  run;
```

```

      end;
run;

proc summary data = auctree noprint;
  var auc;
  output out = aucest sum = auCL;
run;

proc sort data = auctree out = part1 nodupkey ;
  by subject ;
run;
data AUCs&i (keep = subject period auCL);
  merge part1 aucest;
run;
%mend auc;

```

The following macro can be used to perform estimation according to Trapezoidal Rule:

```

%macro trap(a,b,n, function);
  data f1;
    do i = 0 to &n ;
      if i = 0 then do;
        x = &a ;
        y = ((&b - &a)/&n )*( &function / 2 );
        output;
      end;
      else if i = &n then do;
        x = &b ;
        y = ((&b - &a)/&n )*( &function / 2 );
        output;
      end;
      else do;
        x = ( &a + i * (( &b - &a) / &n ) );
        y = ((&b - &a) / &n) * &function;
        output;
      end;
    end;
  end;
run;
proc summary data=f1;
  var y;
  output out=p1 sum=areau;run;
proc print data=p1;
run;
%mend;

```

The Chi-Square/Fisher's exact test can be done using the following SAS code example:

```

PROC FREQ DATA = data;
  TABLES param*trt / CHISQ FISHER EXPECTED;

```

```
WEIGHT count;
RUN;
```

Kruskal Wallis test can be performed in SAS using the following reference code:

```
PROC NPAR1WAY DATA=soil WILCOXON;
  CLASS location;
  EXACT WILCOXON / MC;
  VAR claypct;
RUN;
```

T test within the cross over design in CRC phase can be done with the help of the following reference code:

```
PROC TTEST DATA=data PLOTS=interval;
  VAR aval1 aval2 / CROSSOVER = (TrtA TrtB);
RUN;
```

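### SAP 4.3.7 and 4.3.8 assign ANOVA/Kruskal-Wallis to the CGM percent-time measures with no separate rule for the CRC crossover, so following the text ignores the pairing and makes those CRC tests conservative

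*SAP*

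**What the plan says.** SAP 1.2 describes the CRC phase as a "two-treatment, two-period, crossover comparison in a clinical research center (CRC) setting". SAP 1.3.1 confirms the pairing: "At the second session, the subject will be crossed over to the other treatment assignment".

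The CGM measures are analysed in that phase. The secondary endpoint for glucose below range is "measured by unblinded CGM (inpatient and outpatient". Exploratory items 2 and 3 (above 180 and above 250 mg/dL) name both the CRC and the outpatient arms. Exploratory item 1, time in range, is limited to "CGM, 0 to 300 minutes with exercise), across the 2 CRC treatment arms". SAP 5.1 lists CRC tables for time in hypoglycemia (14.2.4.5.3.1 and .2), glucose within range (14.2.4.5.5.1 and .2) and glucose above range (14.2.4.5.6.1 and .2). Within-range glucose has no outpatient table.

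The tests are set once, for both phases together. Section 4.3.7 on percent time below 54 mg/dL: "percentage within serious hypoglycemia <54 mg/dL (3 mmol/L)) will be calculated and treatment difference will be calculated using ANOVA/Kruskal–Wallis test", the choice depending on normality. Section 4.3.8: "Time and Proportional time (percentage within range, >180 mg/dl, >250 mg/dl) will be calculated and treatment difference will be calculated using ANOVA/Kruskal–Wallis test", on the same condition.

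Methods that respect pairing appear elsewhere in the SAP:
- Appendix 2 says a "T test within the cross over design in CRC phase can be done" and gives PROC TTEST code with a crossover option.
- Section 4.3.6 names Friedman's test and a sign test, under the outpatient primary endpoint.
- Appendix 3 has a PROC MIXED example with a random subject term, as the ANCOVA example; section 4.3.8 ties ANCOVA to mean incidence rates.

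The text assigns none of these to the percent-time measures.

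**The concern.** The comparison of interest in the CRC phase is within subject: glucagon session against placebo session. Kruskal-Wallis takes its null distribution from shuffling treatment labels over all sessions as if each came from a different person. A treatment-only ANOVA uses the total between-subject variance as its error term. Neither uses the pairing that the crossover was built to provide.

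Two features make this more than loose wording. First, the SAP compares time in range only across the two CRC treatments, so the rule for that measure cannot be read as an outpatient rule, and it is the only test the measure gets. Second, the same sections do split by phase elsewhere: the questionnaires and the exercise and tablet measures are given t tests for the CRC phase and ANOVA for the outpatient phase. The percent-time measures have no such split.

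At stake is the blinded glucagon-versus-placebo comparison on CGM. A conservative test can miss a real reduction in low glucose. For time above 180 and 250 mg/dL conservatism does not protect either, because it can hide excess high glucose on glucagon.

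**Working it through.** **The plan's own figure.** The only power statement (Protocol 12.2, SAP 1.3) is for the outpatient primary endpoint. Its effect size is 59/15² = 59/225 = 0.262. With three groups and alpha 0.05, a noncentral F calculation gives 78.9% power at 13 per group and 82.3% at 14, so 14 per group is reproduced. For attrition, 42 × 1.15 = 48.3 and 42/0.85 = 49.4, against 48 stated. No SD, effect or within-subject correlation is given for any CRC CGM measure, so rho is varied below.

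**Near-normal data.** With n subjects, session SD σ and correlation rho:
- SE assumed by the independent-samples test: σ√(2/n)
- true SE of the treatment difference: σ√(2(1−rho)/n)
- real two-sided alpha of the unpaired test: 2[1 − Φ(1.96/√(1−rho))]
- power of the unpaired test when the paired test has power P: Φ(z_P + 1.96 − 1.96/√(1−rho))

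Worked case, rho = 0.5, P = 0.80: 1.96/√0.5 = 2.772. Alpha = 2[1 − Φ(2.772)] = 0.0056. Power = Φ(0.842 + 1.960 − 2.772) = Φ(0.030) = 0.512.

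| rho | real alpha | power if paired is 80% (loss) | power if paired is 90% (loss) |
|---|---|---|---|
| 0 | 0.050 | 80% (0) | 90% (0) |
| 0.2 | 0.028 | 73% (7) | 85% (5) |
| 0.3 | 0.019 | 68% (12) | 82% (8) |
| 0.5 | 0.0056 | 51% (29) | 68% (22) |
| 0.7 | 0.0004 | 22% (58) | 37% (53) |

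Simulation with 48 pairs and rho 0.5 agrees. Null rejection is 0.005 for ANOVA and 0.008 for Kruskal-Wallis. Power is 52% for ANOVA against 80% for the paired t, and 49% for Kruskal-Wallis against 77% for the signed-rank test.

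**Large effects.** At rho 0.5 and a shift of 0.8 SD, Kruskal-Wallis reaches 99% and the signed-rank test 100%, so almost nothing is lost.

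**Mostly-zero data.** Percent time below 54 mg/dL is likely to be zero in most sessions. The nearest figure is in Protocol 4.2: in the pilot, 5 of 15 subjects in the insulin-reduction arm reached 70 mg/dL or lower, so 10 of 15 (67%) did not reach even that threshold. That was not a 0–300 minute CGM measure, so it is only indicative. With 5–20% of sessions non-zero and latent rho 0.3–0.5, the observed correlation falls to 0.08–0.32. Simulated power at N = 48 and a latent shift of 0.4 SD:

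| zeros | rho | Kruskal-Wallis | signed-rank |
|---|---|---|---|
| 80% | 0.3 | 23% | 23% |
| 80% | 0.5 | 22% | 30% |
| 90% | 0.3 | 14% | 10% |
| 90% | 0.5 | 14% | 11% |

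Across the runs in this setting, Kruskal-Wallis rejects a true null about 2% to 4% of the time. At 90% zeros, rho 0.5 and a 0.8-SD shift, power is 40% for Kruskal-Wallis, 25% for the signed-rank test and 42% for the rank-sum test on period differences. The choice of paired rank test therefore matters.

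**The case against.** The strongest reply is that paired analysis may already be intended. Appendix 2 serves the secondary endpoints and labels its crossover t test for the CRC phase. The questionnaires are completed only at Visit 3 and follow-up, so they cannot use it, and the CGM measures are the secondary endpoints with data from both CRC sessions. ANOVA for CRC data has no stated terms; the treatment-only code is in Appendix 1, for the outpatient primary. This has weight for near-normal measures, and a reader who infers that the SAP contains no paired method would be wrong. It does not settle the matter. The code is offered as something that can be used, the text does not assign it to these measures, and it covers only the normal branch. Kruskal-Wallis cannot carry a subject term, and its sample code has only a class variable. Friedman's test is a paired rank method, but it sits under the parallel-group primary analysis.

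A reader might also infer that these tests run far below 5% and cost some 30 points of power. The documents do not support that as a general statement. It needs rho near 0.5, about 80% paired power and near-normal data, and it does not describe percent time below 54 mg/dL. Nor can one say that reported intervals will be too wide, because 4.3.7 and 4.3.8 promise none for these measures. With positive rho the error is toward missed differences, not false positives.

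**Conclusion.** The point stands as a gap in specification with a known direction. As written, 4.3.7 and 4.3.8 apply an independent-samples rule to crossover data, most clearly for time in range. With positive rho the CRC tests are conservative and usually lose power.

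The size rests on assumed values of rho. For near-normal measures and 80% paired power the loss runs from about 7 points (rho 0.2) to 58 (rho 0.7), with real alpha from about 0.028 to 0.0004. It is near zero for very large effects, and roughly 0 to 8 points at 80–90% zeros and rho 0.3–0.5. The measures are secondary and exploratory. The outpatient primary comparison is parallel-group and unaffected. The change should be made, but the trial's main conclusion does not depend on it.

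**What to change.** In SAP 4.3.7 and 4.3.8, restrict ANOVA/Kruskal-Wallis to the outpatient phase. For each continuous CGM measure in the CRC phase:
- Judge normality on the within-subject glucagon-minus-placebo differences.
- If acceptable, use the Appendix 2 crossover t test, or a mixed model with treatment, period and sequence fixed and subject random.
- If not, use the Wilcoxon rank-sum test on period differences (period 1 minus period 2) between the two sequences, with a Hodges-Lehmann estimate and 95% CI. The shift between sequences is twice the treatment effect, so halve it.
- Do not use the signed-rank test for zero-heavy measures such as percent time below 54 mg/dL, where it can have less power than Kruskal-Wallis.

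Revise Appendix 2 to match, so that the Kruskal-Wallis sample code is labelled for the outpatient phase and the CRC rank test has its own example.

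The cost is SAP wording and a few lines of SAS, with no new data or subjects. One small downside: subjects with only one CRC session drop out of the rank test, although the mixed model keeps them.
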